8.2.7. Pregnancy

Pregnancy testing must be performed on all women of childbearing potential (WOCBP) at the time points specified in the SoA (Section 1.3). Pregnancy tests (local urine testing will be standard unless serum testing is required by local regulation or ethic committees may also be performed at any time during the study at the Investigator's discretion.

WOCBP must have a negative pregnancy test (serum if required per country regulations) before study intervention administration.

- Details of all pregnancies in female participants and, if indicated, female partners of
 male participants will be collected after the start of study intervention and until
 termination of the pregnancy.
- If a pregnancy is reported, the Investigator should inform Alexion within 24 hours of learning of the pregnancy and should follow the procedure outlined in Section 10.5.
- Abnormal pregnancy outcomes (eg, spontaneous abortion, fetal death, stillbirth, congenital anomalies, ectopic pregnancy) are considered SAEs. Pregnancy alone is not considered an AE.
- If a participant becomes pregnant, the study intervention must be immediately discontinued, and Alexion must be notified as per Section 10.5. Each pregnancy will be followed to term and Alexion should be notified regarding the outcome (Section 10.5.3).

8.2.8. Participant Safety Card

Before the first dose of the study intervention, a Participant Safety Card will be provided to participants to carry with them at all times until 5.5 terminal half-lives (8 months) after the final dose of ravulizumab. The card is provided to increase participant awareness of the risk of meningococcal infection and promote quick recognition and disclosure of any potential signs or symptoms of meningococcal infection experienced during the course of the study and to inform participants on what actions must be taken if they are experiencing signs or symptoms of infection.

At each visit throughout the study, the study staff will ensure that the participant has the Participant Safety Card (Section 1.3).

8.3. Adverse Events and Serious Adverse Events

The definitions of AEs and SAEs can be found in Section 10.4.

AEs will be reported to the Investigator by the participant (or, when appropriate, by a caregiver, surrogate, or the participant's legally authorized representative).

The Investigator and any qualified designees are responsible for detecting, documenting, and recording events that meet the definition of an AE or SAE and remain responsible for following up AEs that are serious, considered related to the study intervention or study procedures, or that caused the participant to discontinue the study intervention (Section 7).

Procedures for recording, evaluating, follow-up, and reporting AEs and SAEs are outlined in Section 10.4.

8.3.1. Time Period and Frequency for Collecting AE and SAE Information

All AEs and SAEs will be collected from the signing of the ICF until the last visit specified in the SoA (Section 1.3).

All SAEs will be recorded and reported to Alexion or the designee immediately and under no circumstance should this exceed 24 hours, as indicated in Section 10.4. The Investigator will submit any updated SAE data to Alexion within 24 hours of it being available.

Investigators are not obligated to actively seek AE or SAE data after conclusion of the study participation. However, if the Investigator learns of any SAE, including a death, at any time after a participant has been discharged from the study, and he/she considers the event to be reasonably related to the study intervention or study participation, the Investigator must promptly notify Alexion.

8.3.2. Method of Detecting AEs and SAEs

The method of recording, evaluating, and assessing causality of AE and SAE and the procedures for completing and transmitting SAE reports are provided in Section 10.4.

Care will be taken not to introduce bias when detecting AEs and/or SAEs. Open-ended and non-leading verbal questioning of the participant is the preferred method to inquire about AE occurrences.

8.3.3. Follow-up of AEs and SAEs

After the initial AE/SAE report, the Investigator is required to proactively follow-up on each participant at subsequent visits/contacts. All SAEs and adverse events of special interest (AESIs; as defined in Section 8.3.5) will be followed up until resolution, stabilization, the event is otherwise explained, or the participant is lost to follow-up (as defined in Section 7.3). Further information on follow-up procedures is provided in Section Section 10.4.

8.3.4. Regulatory Reporting Requirements for SAEs

• Prompt notification of an SAE by the Investigator to Alexion is essential so that legal obligations and ethical responsibilities towards the safety of participants and the safety of a study intervention under clinical investigation are met.

- Alexion has a legal responsibility to notify both the local regulatory authority and other regulatory agencies about the safety of a study intervention under clinical investigation. Alexion will comply with country-specific regulatory requirements relating to safety reporting to the regulatory authority, IRBs/IECs, and Investigators.
- Suspected unexpected serious adverse reactions (SUSARs) must be reported according to local regulatory requirements and Alexion policy and forwarded to Investigators as necessary.
- An Investigator who receives an Investigator safety report describing an SAE or other specific safety information (eg, summary or listing of SAEs) from Alexion will review and then file it along with the IB and will notify the Institutional Review Board/Independent Ethics Committee (IRBs/IECs), if appropriate according to local requirements.
 - Under the EU CTR 536/2014, events other than SAEs (eg, unexpected events) that may impact the benefit-risk balance should be reported. See definitions in Section 10.4.5.

8.3.5. Medication Error, Drug Abuse, and Drug Misuse

8.3.5.1. Timelines

If an event of medication error, drug abuse, or drug misuse occurs during the study, then the Investigator or other site personnel will report to Alexion or designee immediately but no later than 24 hours of when they become aware of it.

The full definitions and examples of medication error, drug abuse, and drug misuse can be found in Section 10.5.

8.3.5.2. Medication Error

For the purposes of this clinical study, a medication error is an unintended failure or mistake in the treatment process for a study intervention that either causes harm to the participant or has the potential to cause harm to the participant.

8.3.5.3. Drug Abuse

Drug abuse is the persistent or sporadic intentional, non-therapeutic excessive use of study intervention for a perceived reward or desired non-therapeutic effect.

8.3.5.4. Drug Misuse

Drug misuse is the intentional and inappropriate use (by a study participant) of study intervention for medicinal purposes outside of the authorized product information, or for unauthorized study intervention, outside the intended use as specified in the protocol, including deliberate administration of the product by the wrong route.

8.3.6. Adverse Events of Special Interest

Meningococcal infections will be recorded as AESIs.

8.4. Treatment of Overdose

For this study, any dose of ravulizumab greater than that specified in the protocol will be considered an overdose. If dose cannot be established during the Randomized Controlled Period due to blinding, suspected overdose should be defined by the volume administered.

Overdoses are medication errors that are not considered AEs unless there is an untoward medical occurrence resulting from the overdose.

Alexion does not recommend specific treatment for an overdose.

In the event of an overdose or suspected overdose, the Investigator or treating physician should:

- Capture and forward the event, with or without associated AEs, to Alexion Global Patient Safety via email or facsimile ([contact] or [name]) using the Alexion Clinical Study Overdose Report Form within 24 hours of awareness.
- Contact the Alexion Medical Monitor or designee immediately.
- Closely monitor the participant for any AE/SAE.
- Obtain a plasma sample for PK analysis if requested by the Alexion Medical Monitor or designee (determined on a case-by-case basis).
- For unblinded participants, document the quantity of the excess dose as well as the duration of the overdose in the eCRF.

Decisions regarding dose interruptions or modifications will be made by the Investigator in consultation with the Alexion Medical Monitor or designee based on the clinical evaluation of the participant.

8.5. Pharmacokinetics and Pharmacodynamics

- Blood samples for determination of serum drug concentrations and serum free and total C5 will be collected before and after administration of study intervention at the time points specified in the SoA (Section 1.3) according to applicable regulations.
- Instructions for the collection and handling of biological samples will be provided by Alexion. The actual date and time (24-hour clock time) of each sample will be recorded on the eCRF and the central laboratory requisition form.
- Samples collected for analyses of ravulizumab serum concentration may also be used to evaluate safety or efficacy aspects related to concerns arising during or after the study.
- Baseline and trough PK/PD blood samples will be collected at predose, within 90 minutes before administering study intervention at visits specified in the SoA (Section 1.3). The predose blood sample may be drawn through the venous access created for the dose infusion, prior to administration of the dose.
- Post-dose PK/PD blood samples will be collected post-dose, within 60 minutes after completing study intervention infusion. The post-dose blood samples will be drawn from the participant's opposite, non-infused arm.

- PK/PD blood samples collected at the ET/EOS visit and at Unscheduled Visits will be collected at any time.
- In the event of an Unscheduled Visit, a PK/PD blood sample will be collected anytime.
- Additional information on sample collection, including blood volume requirements, is provided in the Laboratory Manual.

Study intervention concentration information that may unblind the study will not be reported to investigative sites or blinded personnel.

8.6. Genetics

Genetics are not evaluated in this study.

8.7. Biomarkers

Please refer to the Laboratory Study Manual for details on sample collection, including blood volume requirements. Biomarker samples may be analyzed after study completion by the absolute value and change from baseline.

8.7.1. Blood Exploratory Biomarkers

Blood (serum and plasma) samples for biomarker research will be collected from all participants at the time points specified in the SoA (Section 1.3) according to applicable regulations.

Biomarkers to be measured may include, but are not limited to, assessments of the following:

- Complement pathway dysregulation (eg, soluble C5b-9 etc)
- Myositis-specific autoantibodies (eg, antimelanoma differentiation-associated protein 5 [anti-MDA5], antinuclear matrix protein 2 (anti-NXP2/MJ), anti-synthetase/Jo-1, etc)
- Soluble biomarkers including inflammatory and prognostic markers (eg, IL6, KL6, etc)

8.7.2. Additional Biomarker Research

Remaining samples from PK, PD, immunogenicity, and biomarker testing will be stored for additional method developments of assays (eg, prognostics and/or companion diagnostics related to the study intervention target, disease process, pathways associated with disease state, other complement related diseases, and/or mechanism of action of ravulizumab).

Samples will be retained for up to 25 years after termination of the study or other period as per local requirements.

8.8. Immunogenicity Assessments

Antibodies to ravulizumab (ie, ADAs) will be evaluated in serum samples collected predose (90 minutes prior to the start of infusion of study intervention) from all participants according to the SoA (Section 1.3) according to applicable regulations. Additionally, serum samples should also

be collected at the final visit from participants who discontinued the study intervention or were withdrawn from the study. These samples will be tested by Alexion or Alexion's designee.

Serum samples will be screened for antibodies binding to ravulizumab and the titer of confirmed positive samples will be reported. Other analyses may be performed to further characterize the immunogenicity of ravulizumab.

The detection and characterization of antibodies to ravulizumab will be performed using a validated assay method by or under the supervision of Alexion. Antibodies may be further characterized and/or evaluated for their ability to neutralize the activity of the study intervention(s). Samples may be stored for a maximum duration according to local regulations following the last participant's last visit for the study at a facility selected by Alexion to enable further analysis of immune responses to ravulizumab.

8.9. Health Economics Data and/or Medical Resource Utilization

Information regarding outpatient medical visits and hospitalization will be collected in the eCRF by the Investigator and study-site personnel for all participants throughout the study.

This data may be used to conduct exploratory economic analyses.

8.10. Other Assessments and Procedures

8.10.1. Medical History and DM History and Diagnosis

The Principal Investigator or Sub-Investigator will review the participant's medical history including DM history and diagnosis.

The following will be evaluated and documented at the Screening Visit and/or other visits as specified in the SoA (Section 1.3).

• Date of first diagnosis with DM.

9. STATISTICAL CONSIDERATIONS

9.1. Statistical Hypotheses

The null hypothesis associated with the primary endpoint is that there is no difference in TIS40 response rates between ravulizumab and placebo at Week 26 (Part A) or Week 50 (Part B). The alternative hypothesis is that the response rates are different.

9.2. Sample Size Determination

9.2.1. Part A

A total number of 36 participants will be randomized into the study with a 2:1 (ravulizumab:placebo) allocation ratio to ensure approximately 80% power to detect a difference (ravulizumab—placebo) of 45% in TIS40 response rates with a 2-sided Type 1 error of 0.2, assuming the placebo response rate of 23% and approximately 20% dropout rate.

The sample size was calculated in PASS2022 using the 2-sample test for the difference of proportions with a pooled estimate of variance for the primary endpoint (TIS40).

9.2.2. Part B

A total number of 114 participants will be randomized into the study with a 2:1 (ravulizumab:placebo) allocation ratio to ensure approximately 90% power to detect a difference (ravulizumab–placebo) of 35% in TIS40 response rate with a 2-sided Type 1 error of 0.05, assuming the placebo TIS40 response rate of 23% and approximately 20% dropout rate. The sample size was calculated in PASS2022 using the 2-sample test for the difference of proportions with a pooled estimate of variance for the primary endpoint (TIS40).

An unblinded sample size re-estimation is planned to possibly increase the sample size to a maximum of 150 participants in Part B. The maximum sample size may be updated once the primary analysis of Part A is completed (Section 9.5).

9.3. Populations for Analyses

The analysis sets are defined in Table 17. Unless otherwise specified, the same definitions will be used for the statistical analyses of Part A and Part B where applicable.

Table 17: Study ALXN1210-DM-310 Analysis Populations

| Population | Description |
|------------------------|---|
| Randomized Set | All randomized participants grouped by randomized treatment group (for reporting disposition, demographics, baseline characteristics and efficacy). |
| PK Analysis Set (PKAS) | All participants who receive at least 1 dose of study intervention and have at least 1 post-dose PK sample |
| PD Analysis Set (PDAS) | All participants who receive at least 1 dose of study intervention and who have evaluable free or total C5 data |

| Population | Description | |
|---|---|--|
| Per Protocol Set (PPS) (applicable for Part B only) | All randomized participants without any major protocol deviations ^a that could impact the interpretation of efficacy. The PPS will be used for supplemental analyses of the primary and secondary efficacy endpoints. | |
| Safety Set (SS) | All participants who receive at least 1 dose of study intervention. Participants will be analyzed according to the study intervention they actually received. The SS will be used for the analysis of safety data. | |
| OLE Set | All randomized participants who received at least 1 dose of ravulizumab starting from Week 26 (Part A and Part B) onward. | |
| Immunogenicity Analysis Set (IAS) | All participants who receive at least 1 dose of study intervention and have at least one reportable result in the ADA assay. Participants will be analyzed according to the study intervention they actually received | |

Table 17: Study ALXN1210-DM-310 Analysis Populations

9.4. Statistical Analyses

Statistical methods described in this section will be further detailed in separate SAPs for Part A and Part B for both RCP and OLE Periods. The SAPs will be developed and finalized prior to the database lock of the Randomized Controlled Period for each part. Statistical analyses will include tabulations of summary data, inferential analyses, by-participant listings, and figures. The summary statistics for continuous variables will include, but not be limited to, the number of participants, mean, standard deviation, minimum, median, and maximum. For categorical variables, frequencies and percentages will be presented.

All efficacy analyses will be based on the randomized set. Supplemental per-protocol analyses for primary and key secondary efficacy endpoints will be performed based on the Per Protocol Set (PPS) in the same manner as for the randomized set. Safety analyses will be performed on the Safety Set (SS).

The baseline value for analysis and reporting will be based on the last non-missing measurement on or prior to the first dose of study intervention unless stated otherwise.

All data collected during the first 26-week Randomized Controlled Period in Part A will be analyzed independently of Part B and not be included in Part B's formal hypothesis testing.

Analyses will be performed using the SAS® software Version 9.4 or higher.

9.4.1. Efficacy Analyses

This section describes the planned analyses for the primary and key secondary endpoints during the Randomized Controlled Periods for Part A and B. Further details will be provided in the separate SAPs for each part.

^a Determination of applicable major protocol deviations for this purpose will be made prior to database lock and study unblinding.

Abbreviations: ADA = antidrug antibody; C5 = complement component 5; OLE = Open-Label Extension; PD = pharmacodynamics; PK = pharmacokinetics

9.4.1.1. Efficacy Analysis of Part A

The statistical testing in Part A will be performed with a 2-sided Type 1 error of 0.2 unless stated otherwise.

The estimated treatment effect, 2-sided p-value, and the 2-sided 80% confidence interval (CI) of the treatment effect will be presented.

9.4.1.1.1. Analyses of Primary Efficacy Endpoint for Part A

The primary efficacy analysis will be based on the Randomized Set.

The primary endpoint is TIS≥40 response at Week 26. For the binary composite estimand described in Section 3.1.1, participants experiencing an intercurrent event will be considered non-responders at Week 26, regardless of available TIS data. For all other participants without an intercurrent event, TIS values at Week 26 will be dichotomized into a binary endpoint.

The differences in proportions, along with 2-sided 80% confidence intervals (CIs) using Chan and Zhang method (Chan, 1999), will be presented between the ravulizumab group and the placebo group. Barnard's unconditional exact method will be applied to test whether there is a difference in the proportions of responders between the 2 treatment groups.

Further details, including but not limited to additional sensitivity analyses will be provided in the SAP for Part A.

9.4.1.1.2. Analyses of Secondary Efficacy Endpoints for Part A

A mixed effect repeated measures model will be used to analyze continuous efficacy endpoints. The analysis as stated for the primary endpoint will be used to analyze binary efficacy endpoints and the Cox proportional hazard model will be used for the survival (time-to-event) efficacy endpoints.

Further details will be provided in the SAP for Part A.

9.4.1.2. Efficacy Analysis of Part B

All data collected during the 50-week Randomized Controlled Period in Part B will be analyzed independently of Part A.

The formal statistical hypothesis testing in Part B will be performed with 2-sided Type 1 error of 0.05.

9.4.1.2.1. Analyses of Primary Efficacy Estimand and/or Endpoint for Part B

The primary efficacy analysis will be based on the Randomized Set.

The primary endpoint is defined as TIS≥40 response at Week 50. For the binary composite estimand described in Section 3.1.1, participants will be considered non-responders after experiencing the intercurrent event, regardless of available TIS data. Missing TIS values from participants without intercurrent events will be handled via multiple imputation (MI) assuming missing at random (MAR).

Cochran-Mantel-Haenszel weighting will be used in the estimation of the difference in proportions between treatment and placebo and its variance where the weights account for the

randomization strata (CDASI Activity Score [\leq 14, >14]). If MI is used, Rubin's rule will be used to combine estimates of the difference in proportions and the standard error across the imputations and used to compute the p-value and 95% confidence interval. A 2-sided Type I error of 0.05 and the computed p-value will be used to determine whether the study is considered positive.

The study will be considered positive if the estimated treatment effect favors ravulizumab and the 2-sided p-value is < 0.05.

Further details, including but not limited to the additional sensitivity analyses and subgroup analyses, will be provided in the SAP for Part B.

The planned interim analysis for the sample size re-estimation may also be conducted as described in Section 9.5.

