All participants completing the OLE Period (130 weeks for Part A or 74 weeks for Part B) will have an End of Study (EOS) Visit at Week 156 (Part A) or Week 124 (Part B) and a follow-up phone call 21 weeks (± 1 week) after the participant's last dose of study intervention to collect information on concomitant medications, non-pharmacologic therapies and procedures, and adverse events (AEs).

Adjustments of 'protocol allowed' DM medications (Section 6.5.1) will be permitted throughout the OLE Period.

Participants who discontinue study intervention are encouraged to complete the visits and assessments of the OLE Period (see Section 7.1).

Participants who discontinue/withdraw from the study will complete an Early Termination (ET) Visit and a follow-up phone call (see Section 7.2).

Participants from Part A (Phase 2) will not be enrolled in Part B of the study (Phase 3).

Disclosure Statement: This is a blinded, parallel group intervention study with 2 treatment arms followed by an OLE Period. Both Part A and Part B follow this design.

Number of Participants: Participants will be screened until enough participants have been enrolled to achieve an estimated total of approximately 36 participants in Part A (24 ravulizumab:12 placebo) and approximately 114 participants in Part B (76 ravulizumab: 38 placebo).

Intervention Groups and Duration: Eligible participants will be enrolled into the study and will be randomized in a 2:1 ratio (Part A) or stratified by cutaneous manifestations CDASI activity score (\leq 14 and > 14) and randomized in a 2:1 ratio (Part B) to receive intravenous (IV) ravulizumab or placebo (Section 6.3.1) within each stratum.

The study intervention dose for each participant will be based on body weight. The dosing regimen for both Parts A and B consists of a loading dose followed by maintenance doses administered every 8 weeks. The maintenance dosing will be initiated 2 weeks after the loading dose is administered.

The Randomized Controlled Period for Part A will be 26 weeks in duration. The Randomized Controlled Period for Part B will be 50 weeks in duration. Participants may continue to receive ravulizumab or for up to 130 weeks (approximately 2.5 years) (Part A) or up to 74 weeks (approximately 1.5 years) (Part B) in the OLE Period, or until ravulizumab is registered or

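### Part B's primary p-value is tied to the confidence-interval standard error of the risk difference; read as a Wald test, it runs at about 5.5-6.0% two-sided instead of 5%, with the excess in ravulizumab's favour

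*Protocol*

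**What the plan says.** Protocol 9.4.1.2 sets the level: "The formal statistical hypothesis testing in Part B will be performed with 2-sided Type 1 error of 0.05". Section 9.4.1.2.1 gives the success rule: "The study will be considered positive if the estimated treatment effect favors ravulizumab and the 2-sided p-value is < 0.05".

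The same section defines the estimator. "Cochran-Mantel-Haenszel weighting will be used in the estimation of the difference in proportions between treatment and placebo and its variance", with weights that reflect the two CDASI strata. If multiple imputation (MI) is used, Rubin's rule is to "combine estimates of the difference in proportions and the standard error across the imputations and used to compute the p-value and 95% confidence interval". No variance formula is named, and further detail is left to a Part B SAP. The SAP supplied covers Part A only.

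Section 9.2.2 sizes the trial: "A total number of 114 participants will be randomized into the study with a 2:1 (ravulizumab:placebo) allocation ratio to ensure approximately 90% power", for a 35-point difference from a 23% placebo rate with about 20% dropout. It adds: "The sample size was calculated in PASS2022 using the 2-sample test for the difference of proportions with a pooled estimate of variance". The Synopsis gives the arms: "approximately 114 participants in Part B (76 ravulizumab: 38 placebo").

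**The concern.** One standard error serves both the p-value and the confidence interval. A standard error meant for an interval cannot assume that the two arms respond equally, so the p-value is in effect the estimate divided by a non-null standard error.

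With 2:1 allocation and a low response rate, that form is lopsided. The placebo arm is half the size of the ravulizumab arm and contributes most of the variance. If placebo happens to respond poorly, the observed difference grows and its estimated variance shrinks at the same time. False positives therefore collect on the side that declares the drug effective.

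This p-value alone decides whether Part B is positive. Under 9.4.1.2.5 it also decides whether the key secondary endpoints are tested.

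**Working it through.** **Inputs.** From the protocol: 76:38, two-sided 0.05, 23% against 58%, 20% dropout, two CDASI strata, and a maximum of 150 participants. Assumed, because the documents do not say: the split between strata (50:50, 33:67 and 20:80 tried) and the missing-data pattern.

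**Step 1: the plan's sample size.** With pooled variance and ratio 2, the average rate is (2 × 0.58 + 0.23)/3 = 0.463. The placebo number is

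[1.960 √(0.463 × 0.537 × 1.5) + 1.282 √(0.58 × 0.42/2 + 0.23 × 0.77)]² / 0.35² = 29.4, so 30.

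That means 30 + 60 = 90 evaluable, with power 0.906. For dropout, 30/0.8 = 37.5, so 38 placebo and 76 ravulizumab: 114. The stated figure reproduces.

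**Step 2: one table that shows the mechanism.** Take 20/76 responders on ravulizumab and 4/38 on placebo, a difference of 0.263 − 0.105 = 0.158.
- Unpooled variance: 0.263 × 0.737/76 + 0.105 × 0.895/38 = 0.00503. SE 0.0709, z = 2.23, p = 0.026.
- Pooled variance (24/114 = 0.211): 0.211 × 0.789 × (1/76 + 1/38) = 0.00656. SE 0.0810, z = 1.95, p = 0.051.

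**Step 3: exact error, one stratum.** The probabilities of all 77 × 39 tables were summed, with the same response rate in both arms.

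| Setting | Variance | Favours ravulizumab | Favours placebo | Two-sided |
|---|---|---|---|---|
| 76:38, 23% | unpooled | 3.66% | 2.13% | 5.79% |
| 76:38, 23% | pooled | 2.16% | 2.70% | 4.86% |

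The favourable tail with the unpooled variance is about 4.1% at a 15% rate. At 23% it is 3.56% with 100:50 (the maximum of 150) and 2.78% with 57:57. Most of the one-sided excess therefore comes from the 2:1 allocation.

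**Step 4: the stratified estimator.** In stratum k the weight is w = n_T n_C/(n_T + n_C), and the estimate is Σw(p_T − p_C)/Σw. Its variance is Σw²V/(Σw)², where V is one of:
- unpooled: p_T(1 − p_T)/n_T + p_C(1 − p_C)/n_C
- n−1: the same with n − 1 in each denominator
- null: p(1 − p)(1/n_T + 1/n_C), with p the rate pooled over arms in the stratum

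Sato's variance, which has its own formula for the whole sum, was also tried. Results at 76:38 and 23% in both strata, by simulation (1,000,000 trials per split):

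| Variance | Two-sided | Favours ravulizumab |
|---|---|---|
| unpooled | about 6.0% | 3.8% |
| Sato | 5.8% | 3.7% |
| n−1 | 5.5-5.6% | 3.5-3.6% |
| null | 5.0-5.1% | 2.2-2.3% |

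The split between strata barely matters. Other runs put the favourable tail as low as 3.4% for the non-null variances and as high as 2.4% for the null variance.

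**Step 5: with MI and Rubin's rule.** With the unpooled variance, one set of runs (5-20% missing, null rates 15-30%, 30 imputations) gave 6.0-6.3% two-sided. Another (20% missing, 23%) gave 5.6% when response was imputed with a uniform prior and 6.1% with a Jeffreys prior. The protocol does not give the imputation model, so 5.6-6.3% is the fair range.

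**Step 6: price of the null variance.** Twenty percent loss leaves 0.8 × 76 ≈ 61 and 0.8 × 38 ≈ 30. Exact one-stratum power at 58% against 23% is 92.0% unpooled and 90.9% pooled.

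**The case against.** The strongest reply is that the defect is inferred. The protocol names no variance, its Rubin's-rule sentence applies only if MI is used, and details are left to a Part B SAP that is not among the documents. The summary of changes describes the revised method as a CMH test, which is a null-variance test. Section 9.4.1.2.5 also says that inference will account for the sample size re-estimation so as to control the overall error, so the final statistic may not be fully fixed. All of this stands as a limit on certainty. It does not remove the point, because the current text ties the p-value to the combined difference and standard error, and every usual interval-type variance tried exceeds 5%.

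Three stronger readings are not supported:
- A reader might infer that the confirmatory test certainly runs at 6%. The n−1 variance gives about 5.5%, and a null variance in the Part B SAP would bring the error back to about 5%.
- A reader might infer that MI makes matters clearly worse. The missing fraction is also uncertain: participants with the listed intercurrent events count as non-responders and are not imputed, and those who stop treatment are still followed.
- A reader might infer that the sample size is wrong because it used another variance. The figure of 114 reproduces, and sizing with one variance and testing with another is not in itself an error.

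**Conclusion.** The concern holds in a limited form. Followed as written, 9.4.1.2.1 leads to a test whose two-sided error is about 5.5-6.0% at the planning rate: 0.5 to 1 point above the stated level. The favourable tail is 0.9 to 1.3 points above its nominal 2.5%. The excess persists at 150 participants treated as a fixed size.

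This rests on reading the text as a Wald test with a non-null variance, on a common response rate near 23%, and on the assumed stratum splits. The unblinded re-estimation was not modelled. It is a should-fix point: modest in size, but it falls on the side that declares efficacy, in the one test on which the trial's claim depends.

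**What to change.** State in 9.4.1.2.1 and in the Part B SAP:
- The CMH-weighted difference remains the estimate.
- The p-value uses the null variance of that difference, pooled over arms within each stratum, calculated in each imputed data set and combined with the difference by Rubin's rule. Without MI this is essentially the CMH test.
- The 95% confidence interval may keep the non-null standard error, with a note that it can occasionally disagree with the test. When there is no MI, a stratified score interval may be used instead. Rubin's rule combines an estimate and its standard error, so it does not directly supply a CMH chi-square or a score interval.

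The null variance is not exact either: one MI run with 20% missing put the two-sided error at 5.3%. The Part B SAP should confirm the level by simulation with its own imputation model and the re-estimation rule.

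The cost is a wording change and about one point of power (92% to 91% with 20% loss). Sample size and data collection do not change.
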